5.4.6 Checking model assumptions

The key assumptions for the above model to be applicable are linearity of the concentration-QTc-relationship and the absence of hysteresis. These assumptions apply only if there is an effect of plasma concentrations on QTc. Therefore, if the predictions described above exclude an effect of more than 10 ms (i.e. the two-sided 90 % confidence interval for the prediction is completely below 10 ms) and

the per timepoint analysis described in 5.4.4 do not indicate a different result, the primary model will be accepted.

If, however, a prolongation beyond 10 ms cannot be excluded, the following will be performed:

Hysteresis: Simultaneous displays of the time courses of the placebo adjusted mean $\Delta QTcF$ ($\Delta\Delta QTcF$) and the (arithmetic) mean plasma concentrations will be prepared. Likewise, hysteresis loops, i.e. a plot of mean $\Delta\Delta QTc$ against the mean concentration for each timepoint will be presented. If there is a delay of the maximum of the mean $\Delta\Delta QTcF$ with respect to the mean concentration of all moieties included in the primary model, this is an indication for hysteresis. If there is a delay, it will be assumed that the model used is not appropriate.

Linearity: Linearity will be assessed from the decile plots (see below). In addition, if the treatment effect of all candidate models is significant on the 5 % level, a nonlinear e_{max} model will be fitted to the data. More specifically, this will be a model where each of the concentration terms in the linear model with lowest AIC is replaced by an e_{max} -term $aC(1+bC)$. In this model the only random effect per subject will be the intercept. Predictions will be based on this model or on the primary linear model, whichever fits better according to the Akaike Information Criterion and the t-value of the treatment effect. More specifically, if the e_{max} model has a non-significant treatment effect, while the linear one has a significant one, the e_{max} model will be used, otherwise, the one with the smaller AIC will be used.

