10.4.3 Concentration-QTc analysis

This analysis will be based on the change of QTc from baseline and will use baseline QTc and the concentrations of AQ, DEAQ and relevant analytes/metabolites (when AQ administered alone and in combination with ATV-PG) as covariates. Treatment and time will be used as discrete fixed effects. A series of linear models including one or more of the concentrations will be fitted and the most appropriate one will be selected based on the AIC (Akaike Information Criterion) and the size of the fixed treatment effect. A significant treatment effect (based on an F-test) will be considered an indication for model misfit. For the best fitting linear model, predictions of the effect on QTc will be made at the mean concentrations of the moieties involved at the t_{max} for each of these moieties.

If the per-timepoint analysis described above excludes an effect exceeding 10 ms – i.e. the all confidence intervals are below this value – the best fitting linear model will be accepted. If this is not the case and the best fitting linear model has a significant treatment effect, nonlinear e-max models will also be considered, and predictions will be made based on the best fitting model. In this case, hysteresis between QTc and the concentrations of the relevant analytes and metabolites will be investigated graphically.

Absence of an effect of concern of the IMP on QTc will be concluded if the predictions based on the best-fitting model at the concentrations described above exclude an effect exceeding 10 ms, i.e. the upper limit of the two-sided confidence interval for these predictions is below 10 ms.

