5.4.4 By timepoint analysis for QTc

A linear model of the form: $\Delta QTc \sim \text{treat} + \text{BL}$ will be fitted for each timepoint and the difference between each of the active treatments and placebo will be estimated based on this model with two-sided 90 % confidence intervals. In this model, treat is a factor with four levels: placebo, the two monotherapies and combination therapy, and BL is the centered baseline (i.e. the mean baseline across subjects is subtracted from each individual baseline).

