5.4.5 Primary linear model

A series of linear mixed effects model will be fitted. The most comprehensive of these models will be of the form

$$\Delta QTcF \sim C_{ATV} + C_{AQ} + C_{PG} + C_{CG} + C_{DEAQ} + \text{treat} + T + BL$$

where $\Delta QTcF$ is the change from baseline of QTcF, C_{ATV} the plasma concentration of ATV, C_{AQ} the plasma concentration of AQ, C_{PG} the plasma concentration of PG, C_{CG} the plasma concentration of CG, C_{DEAQ} the plasma concentration of DEAQ, treat is a four-level factor with levels placebo, ATV-PG, AQ and ATV-PG + AQ (for placebo, the two monotherapies and the combination therapy respectively) and T is a discrete time effect with one level for each timepoint across study days – i.e. the same time at different days will have different values. This model will allow for treatment and time as categorical fixed effect factors. Concentrations of AQ, DEAQ and relevant analytes/metabolites will be used as covariates.

Note that including a treatment effect will allow some judgement on the appropriateness of the model, as a well-fitting linear model should have a non-significant treatment effect. BL is baseline value for each subject, with the mean across subjects subtracted. No fixed intercept will be allowed.

The model will have random effects per subject for the intercept and the concentration levels. An unstructured covariance matrix will be assumed. If this model does not converge, some or all of the random slopes will be removed, and further simplifications may be performed to reach convergence. Parameter estimation will be using the REML (Restricted Maximum Likelihood) method.

The Kenward-Roger approximation will be used to calculate degrees of freedom and any t-test-based quantities, in particular two-sided 90% confidence intervals for the model parameters.

From the above most comprehensive model, simplified models will be derived by omitting one or more concentration parameters. This will be performed in a stepwise way, by removing the concentration with the smallest absolute t-value from the model. As a result, a series of 5 models with 5 down to 1 concentration will be obtained. For each model, the AIC and the F-value of the treatment effect from an ANOVA will be obtained. If this F-value is significant at the 5 % level, the model will be excluded from the candidate set. For the models remaining, the model with smallest AIC will be chosen as primary.

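### SAP 5.4.6 ties the hysteresis checks to a 10 ms result that a delayed effect can bias, and gives its by-timepoint safeguard no criterion

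*SAP*

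**What the plan says.** SAP 5.4.6 names linearity and absence of hysteresis as the key model assumptions, then limits when they matter: "These assumptions apply only if there is an effect of plasma concentrations on QTc". The primary model is accepted without further work if two things hold together:

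- its prediction excludes 10 ms, "i.e. the two-sided 90 % confidence interval for the prediction is completely below 10 ms";
- the analysis that uses no concentration model does not contradict this: "the per timepoint analysis described in 5.4.4 do not indicate a different result, the primary model will be accepted".

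The other branch opens: "If, however, a prolongation beyond 10 ms cannot be excluded, the following will be performed". Under it sit the paired time courses of placebo-adjusted QTcF change and concentration, the hysteresis loops, and an e_max fit if every linear candidate has a significant treatment term. The trigger does not say which of the two analyses must fail to exclude 10 ms. On hysteresis the section ends: "If there is a delay, it will be assumed that the model used is not appropriate". No replacement result is named.

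Protocol 10.4.3 has a different gate. It begins "If the per-timepoint analysis described above excludes an effect exceeding 10 ms", explains this as every interval lying under that limit, and then accepts the best linear model. If that fails and the treatment term is significant, e_max models and graphical hysteresis work follow. The SAP carries notes on its departures from the protocol for heart-rate correction (5.4.1) and assay sensitivity (5.4.8), but none for this change.

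Some fit checks are unconditional. Every candidate model faces a treatment F-test: "If this F-value is significant at the 5 % level, the model will be excluded from the candidate set" (5.4.5). A residual decile plot and goodness-of-fit plots are always produced (5.4.7).

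**The concern.** If the QTc effect lags behind plasma concentration, a model that assumes no lag fits too shallow a slope and predicts too small an effect at C_max. That prediction is the main test of whether the hysteresis displays are made at all, so the fault can switch off the check meant to find it.

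The by-timepoint condition could prevent this, because it uses no concentration term. As written, though, it has no threshold, and the SAP does not say what happens when the model clears 10 ms and the by-timepoint analysis disagrees.

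At stake is the 10 ms statement about QTc, a secondary objective. Lag is a reasonable question here: Protocol section 1 gives median t_max of 0.79 h for AQ and 2 h for DEAQ, with half-lives of 7.9 h and 211 h.

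**Working it through.** The documents give no SD, power or error rate for the QTc analysis, so there is no stated figure to reproduce. The subject count does agree: 20 + 24 = 44 = 8 + 12 + 12 + 12 (SAP 3.1).

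**1. What the by-timepoint condition demands under each reading.** In SAP 5.4.4 a linear model with treatment and baseline "will be fitted for each timepoint and the difference between each of the active treatments and placebo will be estimated". With 44 subjects and 5 parameters (four treatment levels and baseline), df = 39 and t(0.95, 39) = 1.685. The 90% half-width is 1.685 × SD × √(1/n₁ + 1/n₂). The SDs of ΔQTc are assumed.

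| Assumed SD (ms) | 6 | 8 | 10 | 12 |
|---|---|---|---|---|
| Monotherapy v placebo, 12 v 12 | 4.1 | 5.5 | 6.9 | 8.3 |
| Combination v placebo, 8 v 12 | 4.6 | 6.2 | 7.7 | 9.2 |

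Take 12 v 12. If disagreement means an upper limit of 10 ms or more, an estimate of 10 − 4.1 = 5.9 ms (SD 6) or 10 − 6.9 = 3.1 ms (SD 10) triggers the checks. If it means a lower limit of 10 ms or more, the estimate must reach 10 + 4.1 = 14.1 ms or 10 + 6.9 = 16.9 ms. The SAP wording allows either.

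**2. Delayed effect, true peak 12 ms.** Simulation of AQ (12) v placebo (12), 19 post-dose timepoints, 600 runs per scenario. The fit is a random-intercept model with time, treatment and AQ, or AQ + DEAQ. Half-lives come from Protocol section 1. Everything else is assumed:

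- total SD √(5² + 5²) = 7.1 or √(7² + 6²) = 9.2 ms;
- effect-compartment rate 0.3 or 0.1 per h, a delay half-life of ln 2/rate = 2.3 or 6.9 h;
- absorption rates, and 35% log-scale variation between subjects.

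With the prediction taken from the concentration terms only:

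- The mean prediction is 0.1–5.2 ms (AQ only) or 6.0–8.0 ms (AQ + DEAQ), against a true 12 ms.
- The model clears 10 ms and passes the F-test in 5–32% of runs. With no delay and AQ + DEAQ in the model, the figure is about 1% (0.8% and 1.0% at the two SDs).
- If the treatment term is added to the prediction, 5–32% becomes 2–11%. The SAP does not say which form is meant.

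**3. Delayed effect, true peak exactly 10 ms.** Assumed SDs 5 and 7 ms, delay half-lives 2, 4 and 8 h, in two simulations of 400 and 600 runs per delay. In the 400-run simulation the mean prediction is 9.2, 7.8 and 6.9 ms.

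**4. Share accepted without the hysteresis checks** (model clears 10 ms, F-test not significant, by-timepoint condition met):

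| Disagreement means any by-timepoint | Peak 12 ms | Peak 10 ms, 400 runs (2, 4, 8 h) | Peak 10 ms, 600 runs |
|---|---|---|---|
| 90% upper limit ≥ 10 ms | 0% | 0% | 0% |
| point estimate ≥ 10 ms | 0.5–4% | 5, 7, 9% | 7–12% |
| 90% lower limit ≥ 10 ms | 5–28% | 9, 21, 26% | about 18–28% |

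**5. Cost of the strict reading.** With no true effect, AQ v placebo, at least one upper limit reaches 10 ms in about 31–33% of trials (SD 7.1) or 73–74% (SD 9.2).

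**The case against.** A reader might infer that the model clears itself and is then never checked. The documents do not support that. The by-timepoint condition is joined to the model condition and is free of hysteresis bias, and the F-test, decile plot and goodness-of-fit plots do not depend on the 10 ms result. Linearity is therefore partly covered. None of these targets hysteresis, however.

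A reader who simulates only the model's upper bound at a true 10 ms peak might quote 11, 18 and 33% wrongly clearing, for delays of 2, 4 and 8 h. Those figures leave out both the F-test and the by-timepoint condition, so they do not describe the SAP's procedure.

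A reader might also infer that the plan stalls if all five linear candidates fail the F-test. It does not: no prediction then excludes 10 ms, and 5.4.6 provides an e_max model built from the lowest-AIC linear one.

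These further points on the other side have force:

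- DEAQ peaks later than AQ and can absorb some of the lag, as the higher predictions with DEAQ show.
- SAP 5.4 says the by-timepoint analysis has limited power to show absence of an effect. Under the upper-limit reading that makes the gate stricter, not weaker.
- The protocol's hysteresis plots are also conditional, and need a significant treatment term as well. In that respect the SAP's trigger is broader.
- Large effects would open the gate. With AQ + DEAQ in the model, the lower-limit share falls from 8.5–25.7% at a 12 ms peak to 1.2–6.5% at 15 ms. Protocol 1.2.2.1 reports 30.9 ms for QTcF with ASAQ in patients.
- With no effect, the timing of the observed maximum is noise, which is a fair reason not to over-read hysteresis plots.

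These limit the size of the problem. They do not supply the missing criterion.

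**Conclusion.** The concern holds as a gap in the acceptance rule. The hysteresis displays depend mainly on a prediction that hysteresis lowers. The one safeguard free of that bias has no threshold, and it displaces an explicit protocol rule without a note. For delayed effects peaking at 10–12 ms, the share accepted unchecked runs from 0% to about 28%, and the reading of one phrase decides where in that range it falls.

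The range rests on assumed SDs, delays and absorption, on AQ v placebo only, and on models with one or two analytes instead of the SAP's five-analyte stepwise selection. It shows direction and rough size, not an error rate for this trial. The exposure is to effects near 10 ms in a secondary analysis of an exploratory study. The correction is cheap and should be made.

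**What to change.** Amend SAP 5.4.6 as follows, with a note of the departure from Protocol 10.4.3 where one remains:

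1. Produce the paired time courses and hysteresis loops whatever the 10 ms result. This goes further than the protocol.
2. Define disagreement as any by-timepoint two-sided 90% upper limit at or above 10 ms, the criterion in Protocol 10.4.3. State that failure of either condition triggers the further checks.
3. State that, if a delay is seen, the linear model's prediction is not used alone to conclude absence of a 10 ms effect, and that the by-timepoint estimates are reported as the basis for the statement.

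Under rule 2, none of the 600 runs in any scenario with a delayed 12 or 15 ms peak was accepted unchecked.

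The cost is wording, a few plots and possibly one extra fit. The checks will often be triggered with no true effect: about 31–74% of trials for one active arm at the assumed SDs, and more often with three arms compared. An apparent delay can then be chance, and the statement would rest on by-timepoint intervals with the half-widths shown above. The displays should be read with that in mind.

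### SAP 5.4.6 names a nonlinear e_max fallback but prints its term as aC(1+bC), a quadratic with no plateau; a division sign is probably missing

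*SAP*

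**What the plan says.** SAP 5.4.6 sets out checks on the linear concentration-QTc model. They start only under this condition: "If, however, a prolongation beyond 10 ms cannot be excluded, the following will be performed". Under the linearity check, "if the treatment effect of all candidate models is significant on the 5 % level", then "a nonlinear e_{max} model will be fitted to the data". The SAP defines that model as one where "each of the concentration terms in the linear model with lowest AIC is replaced by an" e_max term. With the expression itself, the wording is "replaced by an e_{max} -term $aC(1+bC" (the closing bracket follows in the SAP). On random effects it adds: "In this model the only random effect per subject will be the intercept".

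The choice between the two models is also fixed. If the fallback has a non-significant treatment effect while the linear model has a significant one, "the e_{max} model will be used, otherwise, the one with the smaller AIC will be used".

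SAP 5.4.5 makes the predictions at the geometric means of the individual Cmax values, with two-sided 90% confidence intervals. SAP 5.4.6 and Protocol 10.4.3 judge the upper limit against 10 ms. Protocol 10.4.3 says that "nonlinear e-max models will also be considered" but gives no formula, so the expression in SAP 5.4.6 is the only operational definition of the fallback.

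**The concern.** The name and the formula describe different models. An e_max term rises with concentration and levels off. The printed term is a quadratic, which cannot level off. It is also linear in its coefficients (a and the product ab), so the word nonlinear does not fit it either.

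The fallback exists for the case where a straight line has been rejected, and its prediction can then be the one compared with 10 ms. A programmer who codes the formula literally would base that prediction on a curve that either accelerates or turns over. The first condition for reaching this branch is not remote: Protocol 1.2.2.1 cites a QTcF prolongation of 30.9 ms with artesunate-amodiaquine in patients treated for malaria. The documents give no indication of how likely the remaining conditions are.

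**Working it through.** The plan gives no figure on this point, so there is nothing to reproduce. The check is algebra followed by a numerical illustration.

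**Algebra**

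- Printed term: f(C) = aC(1+bC) = aC + abC². Its slope is a(1+2bC).
- With a > 0 and b > 0 the slope keeps increasing and f has no upper limit.
- With a > 0 and b < 0 the slope is zero at C = −1/(2b), where f = −a/(4b); beyond that f falls. For example, a = 1 and b = −0.25 give a maximum of 1 at C = 2.
- e_max term: g(C) = aC/(1+bC) rises to a/b and is half-maximal at C = 1/b.
- With a = 1 and b = 1, g is 0.50, 0.80, 0.91 and 0.99 at C = 1, 4, 10 and 100. At the same points f is 2, 20, 110 and 10100.

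That comparison shows the difference in shape only. Both parameters are estimated from the data and would take different values under the two forms, so the size of the problem has to come from refitting.

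**Refit**

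Inputs, all assumed because the documents give none: a true, noise-free e_max curve 20C/(1+C) in ms, with C in units of EC50; one concentration term; 401 evenly spaced concentrations from 0 to 1, 2, 4 or 10 times EC50. The printed form and a straight line were each fitted by least squares through the origin. Error is fitted minus true, in ms.

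| Range (× EC50) | a | b | Turning point −1/(2b) | Error at 50% of range | at 60% | at 70% | at top | Largest absolute error: printed form / line |
|---|---|---|---|---|---|---|---|---|
| 0–1 | 17.194 | −0.4346 | 1.15 | +0.06 | +0.13 | +0.14 | −0.28 | 0.28 / 1.58 |
| 0–2 | 14.223 | −0.2804 | 1.78 | +0.24 | +0.42 | +0.43 | −0.84 | 0.84 / 3.13 |
| 0–4 | 10.429 | −0.1652 | 3.03 | +0.63 | +0.99 | +0.96 | −1.85 | 1.88 / 5.02 |
| 0–10 | 5.784 | −0.0747 | 6.70 | +1.46 | +2.02 | +1.83 | −3.53 | 4.65 / 8.28 |

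Two entries worked through for the 0–10 range:

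- At C = 6 the true value is 20 × 6/7 = 17.14. The printed form gives 5.784 × 6 × (1 − 0.0747 × 6), which is 19.16 with unrounded coefficients. The difference is +2.02.
- At C = 10 the true value is 20 × 10/11 = 18.18. The printed form gives 14.65 with unrounded coefficients. The difference is −3.53.

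**Reading the table**

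- The fitted b is negative every time, and the curve turns down inside the range for the three wider ranges.
- The printed form is too high by about 0.1 to 2.0 ms at 50 to 70% of the range and too low by about 0.3 to 3.5 ms at the top.
- The largest error for the widest range, 4.65 ms, occurs at about one tenth of the range, where no prediction is planned.

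**The case against.** **The sign may have been lost when the PDF was read.** A stacked fraction can lose its bar, and the ECG reference-range table in SAP 5.3 is visibly scrambled. Against that, typed slashes survive in the Fridericia and Bazett formulas of SAP 5.3, in the J-Tpeak correction of SAP 5.4.9 and in the half-life formula of SAP 6.2. A slip in the SAP is therefore plausible, but the text cannot settle it. This objection stands as a reason to look at the original first.

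**The intent is clear.** Both documents name an e_max model, and a statistician might supply the slash unprompted. That is likely, and it is the main reason to rate the point minor. The formula is still the only definition given.

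**The fallback may never be used.** This is also fair. Even when it is fitted, the linear model is kept if the selection rule favours it. SAP 5.4.7 adds decile and goodness-of-fit plots, which could expose a poor shape.

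**Stronger readings that do not hold.**

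- A reader might infer that the printed form has no maximum or cannot follow a saturating relationship. With b < 0 it does have a maximum. In the refit it was closer than a straight line, on largest error, over every range tried.
- A reader might take the ratio of the two forms at equal a and b, (1+bC)², as the size of the error: 2.25 at bC = 0.5 and 4 at bC = 1. That compares curves that have not been fitted, and it measures no prediction the trial would report.
- A reader might infer a bias towards finding no effect, because the printed form is too low at the top of the range. Predictions are made at geometric mean Cmax, with some observations above it, and further down the range the error has the opposite sign.

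**Conclusion.** The point holds as a minor error in an operative formula. As the text stands, SAP 5.4.6 contradicts its own model name and Protocol 10.4.3: the term printed is a quadratic without a plateau. Whether the fault lies in the SAP or in the reading of the PDF is open until the original is checked.

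If the term were coded as printed and the fallback selected, the prediction at geometric mean Cmax would be off by roughly 0.1 to 3.5 ms, too high or too low depending on where that concentration falls in the observed range. These sizes rest on an assumed Emax of 20 ms, a range of 1 to 10 times EC50, a single concentration term and no noise. They would scale in proportion to Emax.

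The documents do not show that the 10 ms conclusion would change. In the illustration, at the top of the three wider ranges the true and fitted values are both above 10 ms (13.33 and 12.49, 16.00 and 14.15, 18.18 and 14.65). For the narrowest range they are 10.00 and 9.72, and the decision rests on the upper confidence limit, not on the point prediction.

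**What to change.** Check the expression in the original SAP PDF. If the division sign is there, nothing needs to change. If it is absent, replace the term in SAP 5.4.6 by aC/(1+bC). A bound of b ≥ 0 is optional: it keeps the denominator away from zero (negative b puts a pole at C = −1/b) but is not needed for the correction. The cost is one line of SAP text, best made before the model is programmed. No design, data collection or other analysis is touched.

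### SAP 5.4.6: when the linear and e_max models both fail the plan's own misfit test, AIC still picks one of them for the QTc prediction judged against 10 ms

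*SAP*

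**What the plan says.** SAP 5.4.5 models the change in QTcF on concentrations, a four-level treatment factor, time and centred baseline. Concentrations are removed one at a time, so that "a series of 5 models with 5 down to 1 concentration will be obtained". The treatment factor serves as a diagnostic: "a well-fitting linear model should have a non-significant treatment effect". The rule attached to it is firm: "If this F-value is significant at the 5 % level, the model will be excluded from the candidate set". Among the survivors, the smallest AIC defines the primary model. Protocol 10.4.3 reads the diagnostic the same way: "A significant treatment effect (based on an F-test) will be considered an indication for model misfit".

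SAP 5.4.6 opens its assumption checks under a condition: "If, however, a prolongation beyond 10 ms cannot be excluded, the following will be performed". The e_max model is fitted "if the treatment effect of all candidate models is significant on the 5 % level". Its random effects are restricted: "In this model the only random effect per subject will be the intercept". The linear models of 5.4.5, by contrast, are planned with a random intercept and random concentration effects, an unstructured covariance matrix and REML estimation. Slopes may be dropped if the model does not converge.

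The choice rule in 5.4.6 takes e_max if its treatment effect is non-significant while the linear model's is significant; "otherwise, the one with the smaller AIC will be used". Protocol 10.4.3 then rests the conclusion of no QTc effect of concern on the best-fitting model's predictions, whose upper confidence limit must lie under 10 ms.

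**The concern.** AIC is a relative measure. It says which of two models is better supported, not whether either is adequate. In the final branch both models have failed the test that the plan uses to judge adequacy, and the SAP gives no outcome in which neither is used. The hysteresis check in the same section does have such an outcome: if a delay is seen, the model is taken to be unsuitable.

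The stakes are the 10 ms conclusion. The branch is open only when 10 ms has not been excluded. Under protocol 10.4.3, e_max is considered only when the by-timepoint analysis has not excluded 10 ms, so a poorly fitting model could be set against an unfavourable by-timepoint result. The setting is plausible: protocol 1.2.2.1 cites a prolongation with artesunate-amodiaquine of 30.9 ms by QTcF and 12.5 ms by QTcB.

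Two further weaknesses concern the comparison itself. The two models differ in random-effect structure as well as in curve shape, so the AIC difference does not isolate curvature. REML AICs are also not comparable between models with different fixed effects, and the SAP names no estimation method for e_max.

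**Working it through.** The plan gives no figure for this rule, so there is nothing to reproduce. The main check is the decision logic. The simulations after it are illustrations on assumed values.

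**1. Decision table (SAP 5.4.5 and 5.4.6)**

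| All linear models significant? | e_max significant? | Outcome |
|---|---|---|
| No | not fitted | smallest-AIC surviving linear model |
| Yes | No | e_max |
| Yes | Yes | smaller AIC of the two |

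The AIC rule decides between linear and e_max only in the last row. In that row 5.4.5 has left no candidate, so the primary linear model named in 5.4.6 as the comparator does not strictly exist.

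**2. Covariance parameters**

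A linear model with k concentrations and all random slopes has q = k + 1 random effects and q(q+1)/2 + 1 covariance parameters, including the residual variance. e_max has 2, plus one extra fixed parameter per concentration. The AIC penalty difference under maximum likelihood is 2 × (linear covariance parameters − 2 − k).

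| k | Linear | e_max | Penalty difference |
|---|---|---|---|
| 1 | 4 | 2 | 2 × (4 − 2 − 1) = 2 |
| 2 | 7 | 2 | 2 × (7 − 2 − 2) = 6 |
| 3 | 11 | 2 | 2 × (11 − 2 − 3) = 12 |
| 4 | 16 | 2 | 2 × (16 − 2 − 4) = 20 |
| 5 | 22 | 2 | 2 × (22 − 2 − 5) = 30 |

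The penalty counts against the linear model, while any real between-subject slope variation counts for it. Neither effect bears on linearity.

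**3. Effect of unequal random effects**

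Assumptions: arms of 8/12/12/12 (SAP 3.1), 18 timepoints, one concentration, a true e_max curve plus a 10 ms offset built in to make both models fail, intercept and residual SDs of 6 ms, maximum likelihood, 25 runs per setting. The table gives the share of runs in which AIC chose the linear model.

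| Random-slope SD (ms per concentration unit) | As planned | Both intercept only | Both with slopes |
|---|---|---|---|
| 0 | 16 % | 12 % | 8 % |
| 3 | 84 % | 44 % | 40 % |
| 6 | 100 % | 44 % | 48 % |

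The linear model was significant in all runs and e_max in 84 to 100 %. With 25 runs, a share of 44 % has a standard error of √(0.44 × 0.56 / 25) ≈ 10 percentage points.

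**4. Prediction error when both models fail**

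Two simulations (A: 100 runs, B: 150 runs per scenario) assumed 44 subjects, SDs of 7/7 ms, one analyte (DEAQ) with assumed PK curves, and random-intercept fits. The table shows the error of the linear prediction in ms.

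| Assumed (Emax, EC50) | Slope only, A | Slope only, B | With treatment contrast, B |
|---|---|---|---|
| (15, 0.3) | −8 | −8.2 | +0.4 |
| (25, 0.3) | −13 | −13.2 | −0.2 |
| (40, 1.0) | −10 | −8.5 | +1.1 |

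In A, adding the contrast also brought the error within 2 ms. In A the slope-only 90 % upper limit fell below 10 ms in 96 %, 66 % and 0 % of both-fail runs, although the true peak mean effects were 11, 19 and 20 ms. These figures describe the linear prediction whether or not AIC would have chosen it.

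**5. How often the branch is reached**

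Reading the term as aC/(1+bC), simulation A had all linear fits failing in 76 %, 99 % and 80 % of trials, and both models failing in 23 %, 32 % and 14 %. Given linear failure, e_max therefore failed in 23/76 = 30 %, 32/99 = 32 % and 14/80 = 18 %. Simulation B gave 14 %, 9 % and 9 % when uncertainty in b was carried, and 32 %, 35 % and 19 % when b was treated as known. With the term taken as printed, aC(1+bC), B gave 40 %, 60 % and 15 %. When the linear model was true, both failed in 3 % of runs in A.

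**The case against.** The strongest reply is that this is a narrow gap in a secondary analysis of a study whose sample size rests on no formal considerations (protocol 10.7, SAP 3.3), and that any harm comes from elsewhere. Several parts of that reply stand.

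- **Direction and size.** A reader might infer that the rule understates the QTc effect by around 10 ms. The documents do not support that. SAP 5.4.5 promises predicted effects for each therapy from a model that contains a treatment term, and nowhere says that the term is dropped. With it included, the error nearly vanishes.
- **Frequency.** A reader might infer that the branch is common. The rates depend on assumed PK and effect curves and on the e_max formula. As printed, the term is a quadratic, and a division sign may have been lost in text extraction. Nor were the rates conditioned on the 10 ms gate, although in simulation B the by-timepoint upper limit for AQ exceeded 10 ms at some timepoint in every trial.
- **Which model wins.** Nothing shows that AIC would usually pick the linear one. With equal random effects and the printed term, B had it winning in 67 %, 17 % and 33 % of both-fail trials.
- **Random effects.** The structures coincide if non-convergence removes all slopes, which is plausible with 22 covariance parameters and about 44 subjects. AIC can compare different random structures under full maximum likelihood.
- **Labels.** The missing primary model is largely a naming problem: 5.4.6 builds e_max on the lowest-AIC linear model, which is presumably the comparator. The protocol also speaks of an indication of misfit, not of an invalid model.

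The by-timepoint intervals, decile plots and fit plots will be reported in any case. None of them alters the choice rule, and the final branch remains as written.

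**Conclusion.** The defect in the decision rule holds on the text alone and needs no simulation: the last branch of SAP 5.4.6 is reached only when both models have failed the plan's misfit test, and it still names a winner whose prediction is judged against 10 ms. The mixing of curvature with random-effect structure holds as planned, unless all slopes are removed for non-convergence. The REML point holds wherever AIC compares different fixed effects, including the stepwise series in 5.4.5.

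The size is conditional. On the assumed saturating DEAQ effects, the linear prediction in this state is about 8 to 13 ms too low if formed from the slope alone, and within about 2 ms of the truth if the treatment contrast is included. The SAP does not say which applies. How often the branch arises, and which model AIC would then choose, cannot be fixed from the documents. The point warrants a SAP clarification. It does not show that the planned QTc conclusion is biased.

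**What to change.** Change SAP 5.4.5 and 5.4.6 in three places.

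1. **Final branch.** If all linear models and the e_max model have a significant treatment effect, treat the concentration-QTc model as not appropriate, draw no 10 ms conclusion from it, and answer the question from the by-timepoint 90 % confidence intervals of 5.4.4.
2. **Comparison.** Make any AIC comparison of linear with e_max using the same random effects in both and maximum likelihood, and name the comparator as the lowest-AIC linear model. Confirm the e_max formula at the same time.
3. **Predictions.** State that every prediction includes the treatment-versus-placebo contrast.

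The work is SAP wording, and the by-timepoint analysis is already planned. The price is wider intervals in the both-fail branch; the protocol itself notes that the by-timepoint analysis has limited power to show absence of prolongation. Where the protocol's by-timepoint gate has opened the branch, the answer will be that 10 ms is not excluded. When the linear model is right the cost should be small: both models failed in 3 % of such runs in simulation A.
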